2.2. Epidemiology of DR-TB

South Africa, Ethiopia and Nigeria feature prominently among the 30 high-burden TB countries with significantly overlapping epidemics of TB, Human Immunodeficiency Virus (HIV) and MDR-TB. The 30 high-burden countries collectively contribute to approximately 90% of the global disease burden. South Africa, in particular, remains among the few countries with a TB incidence exceeding 500 cases per 100,000 population with approximately 360,000 cases of TB reported during 2019. In 2019, 13,005 and 406 cases of laboratory confirmed RR/MDR-TB and XDR-TB were reported in South Africa, respectively. The overall treatment success rate was 71% for drug-susceptible TB (DS-TB), 60 % for RR-TB/ MDR-TB and XDR-TB. Ethiopia has a TB incidence rate of 140 cases per 100,000 population with approximately 157,000 cases of TB reported during 2019. In 2019, 658 and 4 cases of laboratory confirmed RR/MDR-TB and XDR-TB were reported in Ethiopia, respectively. The overall treatment success rate was 88% for DS-TB, and 75% for RR-TB/ MDR-TB and XDR-TB. Nigeria records a TB incidence rate of 219 cases per 100,000 population with approximately 440,000 cases of TB reported during 2019. In 2019, 2,384 and 16 cases of laboratory confirmed RR/MDR-TB and XDR-TB were reported in Nigeria, respectively. The overall treatment success rate was 87% for DS-TB, 77% for RR-TB/ MDR-TB, and no data were available for the XDR-TB patients (2).

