6.2. Selection of Participants

Approximately 4800 participants will be screened across the 13 sites (in South Africa, Nigeria and Ethiopia) to enrol 1280 eligible participants. All presumptive TB patients presenting for diagnosis at the study sites will be approached for screening. Each of the sites will also contribute to the historical cohort as described below.

6.2.1. Selection of cohort 1

880 RR-TB (n=440 in SA, n=220 in Nigeria and n=220 in Ethiopia) participants will be enrolled into Cohort 1. Each participant in cohort 1 will be followed up for the duration of TB treatment and passively thereafter to a maximum of 18 months from TB treatment initiation.

6.2.2. Selection of cohort 2

400 HR participants into Cohort 2 (n=200 in SA, n=100 in Nigeria and Ethiopia). Each participant in cohort 2 will be followed up passively for the duration of TB treatment and passively thereafter to a maximum of six months.

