The estimated XDR prevalence among MDR cases is 4.3% in South Africa (2018 Global TB report), 0.6% and 0.7% in Nigeria and Ethiopia (2019 Global TB report). This would mean that N=880*4.3% = 38 XDR cases. As BPaL eligibility extends to pre-XDR patients and treatment intolerant MDR patients, it is expected that a higher number will be on BPaL. A total of 40 participants (including 15% LFU) are needed to detect an improvement from 53% to 85%. This number should be possible for all sites together. Assuming approx. 10% HR-TB in each site, we aim to enrol N=400 in cohort 2 which would allow for approximately 100 HR-TB participants per site, which should be sufficient for studying associated secondary study outcomes.

9.2. Analysis including statistical methods:

Primary endpoint analysis:

- The time to appropriate treatment initiation will be calculated as median days (with interquartile range) between the first sputum collection date and the date of start of the regimen appropriate to the drug resistance pattern (defined as drug-resistance pattern appropriate treatment). This will be compared to the same time in the historical cohort and stratified by geographical location (study site). Confounding will be addressed by multivariable analysis.
- The proportion of favourable study outcomes [treatment cure or completion, based on the WHO definitions (5) will be calculated in the overall study population of cohort 1, and compared with the same proportion in the historical cohort, and stratified by geographical location (study site). In a secondary analysis, these proportions will also be calculated per type of DR-TB. Confounding will be addressed by multivariable analysis.

Both of these outcomes will only be calculated in the primary cohort (cohort 1), as no reliable historical data exist for either endpoint for HR-TB (cohort 2).

Secondary endpoint analysis:

- Prevalence of HR-TB stratified by geographical location. This will be calculated in cohort 2 and stratified by HIV status.
- The incidence of adverse events will be divided into adverse events and serious adverse events and calculated in proportions using both cohort 1 and 2. These will also be stratified by type of DR-TB, treatment regimen, and HIV status.
- Feasibility and acceptability (participant and health care provider perspective), stratified by type of DR-TB regimen (cohort 1 and 2)

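### Section 9.1 expects 38 XDR cases where its own country rates and allocation give about 22, and the look-back window for the historical controls is stated two ways

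*Protocol*

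**What the plan says.** **XDR count.** Section 9.1 first gives country rates: "The estimated XDR prevalence among MDR cases is 4.3% in South Africa (2018 Global TB report), 0.6% and 0.7% in Nigeria and Ethiopia". The next sentence reads "This would mean that N=880*4.3% = 38 XDR cases". Section 6.2.1 sets the cohort 1 allocation: "880 RR-TB (n=440 in SA, n=220 in Nigeria and n=220 in Ethiopia". Section 9.1 then states "A total of 40 participants (including 15% LFU) are needed to detect an improvement from 53% to 85" per cent. It notes that BPaL is also open to pre-XDR and treatment-intolerant MDR patients, that "it is expected that a higher number will be on BPaL", and that the number should be attainable across all sites combined. No rate or count is given for those two groups.

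**XDR definition.** The section 9.1 rates are dated to reports of 2018 and 2019. For the study itself, section 3 adopts the 2021 definition, under which XDR-TB needs fluoroquinolone resistance plus resistance to bedaquiline or linezolid. Section 6.4 excludes strains resistant to any component drug. Section 6.5 adds a late exclusion for BPaL-component resistance found on phenotypic testing after enrolment.

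**Historical cohort.** Table 1 and note 5 to the study schema describe controls from the last two years, about 24 months. Section 6.2.3 describes patients who started treatment within 12 to 18 months before enrolment opens. Only Table 1 gives a size: 220, in a sentence that goes on to refer to each implementing site.

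**The concern.** Two of the three rates are quoted and then not used. Because 38 lies so close to 40, XDR cases alone appear almost to supply the BPaL comparison, and the wider eligibility looks like a margin of safety. With the country rates applied, that margin becomes nearly half of the requirement, and nothing in the protocol puts a figure on it.

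The count also mixes definitions. A case that is XDR by the study's own definition carries bedaquiline or linezolid resistance, which sections 6.4 and 6.5 exclude. A case that is XDR by the older definition need not. Section 9.1 does not say which kind it counts towards the 40.

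The window matters more for the main results. Both primary endpoints compare cohort 1 with the historical cohort, and a 24-month look-back can select different patients, treated under different standard-of-care regimens, from a 12-to-18-month one. The size of that cohort also enters both comparisons.

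**Working it through.** **1. Reproduce the stated count.** 880 × 0.043 = 37.84, which rounds to 38. It is reached by giving all three countries the South African rate.

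**2. Apply each country's rate to its own allocation** (rates from section 9.1, numbers from section 6.2.1).

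| Country | n | Rate | Expected XDR |
|---|---|---|---|
| South Africa | 440 | 4.3% | 18.92 |
| Nigeria | 220 | 0.6% | 1.32 |
| Ethiopia | 220 | 0.7% | 1.54 |
| Total | 880 | | 21.78 |

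37.84 / 21.78 = 1.74, so the stated figure is about 74% too high, or 16 cases. Nigeria and Ethiopia have equal allocations, so the total does not depend on which of the two has 0.6% and which 0.7%.

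**3. Check the 40.** For 53% against 85%, two equal groups, two-sided 5%, 80% power:

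n = [1.96·√(2 × 0.69 × 0.31) + 0.842·√(0.53 × 0.47 + 0.85 × 0.15)]² / 0.32² = 31.6, so 32 per group. 32 / 0.85 = 37.6, so 38 after 15% loss.

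One-sided 5% with 90% power gives 34 per group, and 34 / 0.85 = 40. Section 9.1 states neither the sidedness nor the power for this comparison, but 40 is reasonable and is not disputed.

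**4. Gap to the 40.** Both numbers are enrolled participants before loss, so they compare directly. Stated: 40 − 38 = 2. Recomputed: 40 − 21.8 = 18.2, which is 2.1% of 880.

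**5. Historical window, side by side.** Table 1: about 24 months. Schema note 5: about 24 months. Section 6.2.3: 12 to 18 months. No reading of 12 to 18 months gives 24.

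**6. Which historical n fits the stated power?** Section 9.1 claims 80% power for 74% to 85%, and 90% from a baseline of 71% or less, with 220 enrolled and 15% loss (220 × 0.85 = 187 evaluable). Pooled-variance two-proportion test, two-sided 5%:

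| Historical controls vs evaluable cohort 1 | 74% to 85% | 71% to 85% |
|---|---|---|
| 220 vs 187 (220 controls per 220-person unit) | 78% | 93% |
| 55 vs 187 (220 in total, split like cohort 1; an assumption) | 47% | 64% |
| 220 vs 748 (220 in total, all countries pooled) | 95% | 99% |

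Only the first row is near the stated pair for a 220-person unit, which is the unit that section 9.1 describes.

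**The case against.** **The XDR count is a side remark.** Section 9.1 itself widens the BPaL group beyond XDR, Table 2 proposes BPaL for two regimen classes that include pre-XDR, and the shortfall is only 2.1% of cohort 1. Neither primary endpoint uses the number. All of this stands. A reader might infer that the BPaL comparison will fall short or be underpowered, but the documents do not support that. What remains is that the figure is wrong on its own inputs and that the group which must fill the gap is not quantified.

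**A lower count might be inferred from section 2.2.** It gives 2019 case counts, for example "In 2019, 13,005 and 406 cases of laboratory confirmed RR/MDR-TB and XDR-TB were reported in South Africa, respectively", and dividing these country by country would lead to fewer than 22. But they are counts of reported, laboratory-confirmed cases. Section 2.2 does not say how many RR/MDR cases were tested for second-line resistance, so the ratios are not prevalence among those tested. They should not replace the section 9.1 rates.

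**The older definition can be worked out from the dates.** Reports of 2018 and 2019 precede the 2021 definition. That is a fair inference, and it answers which definition the rates use. It does not settle how XDR cases support a BPaL number when sections 3, 6.4 and 6.5 are read together.

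**The historical n.** A reader might say that it is stated inconsistently, or take the Table 1 wording to mean 220 at every one of the sites. Neither is supported. The figure appears once, so the fault is ambiguity, and nothing else in the protocol points to 220 controls at every site. A loss of power for the primary outcome might also be inferred from the 47% row above, but that row needs 220 to be the total, and the stated power fits about 220 per unit instead.

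**Conclusion.** The point holds in two parts.

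- **XDR count.** The 38 is an error. The protocol's own rates and allocation give about 22, so other BPaL patients must supply about 18 of the 40 rather than 2. The 22 takes rates quoted among MDR cases and applies them to all RR-TB participants, as the protocol does. The effect is confined to a secondary feasibility statement.
- **Historical cohort.** The window is directly contradictory, about 24 months against 12 to 18, for the control group of both primary endpoints. This is the more important part, because the choice determines which controls are selected. The n of 220 is ambiguous. The reading that matches section 9.1 is about 220 per 220-person unit, assuming a two-sided 5% test, outcomes known for all historical controls, and 15% loss in cohort 1 only.

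No shortfall in the primary sample size is shown.

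**What to change.** 1. In section 9.1, replace the 38 by 440 × 4.3% + 220 × 0.6% + 220 × 0.7% = about 22, and say that these rates predate the 2021 XDR definition.
2. In the same paragraph, either give the expected number of pre-XDR and treatment-intolerant MDR patients on BPaL, with its source, or call the 53% to 85% comparison descriptive.
3. Reconcile the use of XDR cases in support of the BPaL number with the definition in section 3 and the exclusions in sections 6.4 and 6.5. How they are reconciled is for the sponsor to decide.
4. Use one historical window in Table 1, schema note 5 and section 6.2.3.
5. State the historical n for South Africa, Nigeria and Ethiopia separately. If the power in section 9.1 is to stand, that means about 220 controls for each 220 participants enrolled in cohort 1.

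The cost is a text amendment, with no added enrolment in the prospective cohorts and no design change. The XDR expectation becomes less favourable, and the BPaL comparison may have to be labelled descriptive.

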Study Duration	48 months: study enrolment will occur over 12 -18 months
Sample Size	A total of 1280 participants will be enrolled between 2 prospective study cohorts: Cohort 1 (newly diagnosed DR; rifampicin resistance [RR-TB] participants; n=880) and Cohort 2 (rifampicin sensitive and isoniazid, fluroquinolone and or second line injectable drug (SLID) resistant participants; HR-TB; n=400). Data from a historical cohort (Cohort 3; n=220) of RR-TB participants that accessed DR-TB care at each implementing site over the last 2 years (approximately 24 months) prior to study start.

Study sites	South Africa (n=2), Nigeria (n=6) and Ethiopia (n=5)
Study population	Adult participants (18 years and over) who test positive for pulmonary M.tb with HR-TB or RR-TB will be approached for study participation
Study intervention	Xpert MTB/XDR assay as a triage test to guide early initiation of an appropriate all-oral DR-TB treatment regimen

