9. STATISTICAL CONSIDERATIONS

9.1. Power and Sample size calculations:

The study will be powered based on the two primary endpoints:

- i) Numbers needed to detect a reduced time to resistance-pattern appropriate treatment initiation for all drug-resistant cases compared to the historical cohort; and
- ii) The difference in proportion of favourable treatment outcomes compared to the historical cohort, allowing for stratification by study site (geographical location).

Current data, mainly from South Africa, show a median time to resistance-pattern appropriate treatment initiation for drug-resistant participants between 15 and 46 days (1-3). With an assumption of an anticipated time to treatment initiation of one week in our study (allowing time for providing repeat sputum samples and delays in Xpert testing), 220 RR-TB participants must be enrolled in cohort one in each country (440 in South Africa), to achieve 90% power to show a shortening of time to treatment initiation. This sample size includes an allowance for an overall 15% loss to follow-up.

Table 6: Reported median times (in days [IQR]) to treatment of drug-resistant TB in literature

Patient type	Xpert-based	LPA-based	Phenotypic DST-based	Location/date	Ref	
All	MDR+XDR	17 [9-47]	38 [23-54]	81 (49-115)	Johannesburg, South Africa 2017	(34)
	RR	0 [0-1]	20 [10-16]	106 [30-124]	Multi-site 2011 (Boehme)	
	MDR	8 [5-25]	50		MSF Cape Town 2015	(35)
	MDR	17 [13-22]	43 [40-46]		Cape Town 2014	(36)
	MDR	15 [1-29]	32 [7-57]		South Africa 2017	(37)

	RR (only 4 pts)	2	21	40 (MGIT)	Cape Town South Africa 2011	
	MDR			88 [29-126]	Korea 2019	(38)
	XDR			97 [79-126]	Korea 2019	(38)
Smear positive	MDR + XDR	15 [1-42]	32 [7-42]	81 [75-107]	Johannesburg, South Africa 2017	
Smear negative	MDR + XDR	-	54 [45-62]	Johannesburg, South Africa	Johannesburg, South Africa 2017	

For the proportion of favourable study outcomes, we used the most recent treatment completion proportions of Kwazulu-Natal province of South Africa, including one of the study sites (4). The average MDR-TB treatment completion proportion is 63%, varying from 57% in their long regimen to 74% using a bedaquiline-based short regimen. The study sample size of n=220 per study site as calculated above will be sufficient to detect an improvement in treatment outcomes with a minimum difference from 74% to 85% (80% power; larger differences with 90% power [from baseline success of 71% and less]), also allowing for 15% loss to follow-up.

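### The 40 participants for 53% to 85% is a per-group size, the historical group it would need is not sized, and an XDR-only comparison would be underpowered

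*Protocol*

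**What the plan says.** Section 9.1 names the second primary endpoint used for sizing: "The difference in proportion of favourable treatment outcomes compared to the historical cohort, allowing for stratification by study site (geographical location"). For the overall outcome it gives a detectable "minimum difference from 74% to 85% (80% power; larger differences with 90% power [from baseline success of 71% and less"].

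It then turns to XDR-TB. It quotes XDR prevalence among MDR cases of 4.3% in South Africa, 0.6% in Nigeria and 0.7% in Ethiopia, and multiplies 880 by 4.3% to expect 38 cases. It adds: "As BPaL eligibility extends to pre-XDR patients and treatment intolerant MDR patients, it is expected that a higher number will be on BPaL". The sizing statement follows: "A total of 40 participants (including 15% LFU) are needed to detect an improvement from 53% to 85" (percent), with the remark that all sites together should be able to supply this number. No alpha, sidedness, power, comparator or source for the 53% is given for this calculation.

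Section 9.2 plans the favourable-outcome comparison with the historical cohort and continues: "In a secondary analysis, these proportions will also be calculated per type of DR-TB". Table 1 gives the size of that cohort: "Data from a historical cohort (Cohort 3; n=220) of RR-TB participants". Its split by country is not stated.

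**The concern.** The sentence calls 40 a total and judges it feasible by counting prospective patients only. If the improvement is measured against historical patients, as the rest of section 9.1 suggests, then 40 has to be compared with a group of some size, and none is given. The treated group is also filled by adding pre-XDR and treatment-intolerant MDR patients, while the reference rate follows directly on an XDR count and is not defined.

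At stake is the only sizing statement for BPaL. A reader would take it that a before-and-after comparison in this subgroup is adequately powered. If it is not, a null result will be uninformative, and a positive one may reflect a different case mix from the patients behind the 53%.

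**Working it through.** **Inputs.** From section 9.1: 53%, 85%, 15% loss, 40 participants, and XDR rates of 4.3%, 0.6% and 0.7%. From section 6.2.1: cohort 1 split 440/220/220. From Table 1: cohort 3, n=220. Alpha is assumed to be 5%. Powers of 80% and 90% were both tried, because section 9.1 uses both for the overall outcome.

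**1. Reproducing the 40.** For two equal groups,

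n per group = [z_α √(2p̄(1−p̄)) + z_β √(p₁(1−p₁) + p₂(1−p₂))]² / (p₂−p₁)²

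with p₁ = 0.53, p₂ = 0.85, p̄ = 0.69, so that the two roots are 0.654 and 0.614 and the denominator is 0.1024.

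- Two-sided 5%, 80% power: (1.960×0.654 + 0.842×0.614)²/0.1024 = 31.6, so 32. Then 32/0.85 = 37.6, so 38 per group.
- One-sided 5%, 90% power: (1.645×0.654 + 1.282×0.614)²/0.1024 = 33.9, so 34. Then 34/0.85 = 40 per group.

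Both groups together: 2×38 = 76, or 2×40 = 80.

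**2. Can 40 be anything else?** The smallest equal-group total among the variants tried is about 54 (one-sided, 80% power, unpooled variance, 26.75 per group after loss). A one-sample test against a fixed 53% needs about 12 to 20 evaluable, or 15 to 24 after loss. If 40 were split over both groups (17 against 17 evaluable), power would be 52% by normal approximation and 39% by Fisher's exact test.

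**3. Historical XDR patients at the protocol's rates.** The last two rows assume a larger cohort 3 than the stated 220.

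| Assumption about cohort 3 | Expected XDR |
|---|---|
| 220, split by 2/6/5 sites | 220×(2×4.3%+6×0.6%+5×0.7%)/13 = 2.7 |
| 220, split equally by country | 220/3×5.6% = 4.1 |
| 220, split 2:1:1 | 110×4.3%+55×0.6%+55×0.7% = 5.4 |
| 220, all at the South African rate | 220×4.3% = 9.5 |
| 220 per country | 220×5.6% = 12.3 |
| Matched to cohort 1, 440/220/220 | 440×4.3%+220×0.6%+220×0.7% = 21.8 |

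**4. Power with 34 evaluable treated (40×0.85), two-sided 5%.**

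| Historical XDR | Fisher exact | Normal approximation |
|---|---|---|
| 3 | 18% | 33% |
| 4 | 28% | 38% |
| 9 | 48% | 54% |
| 12 | 53% | 60% |
| 22 | 70% | 74% |
| 34 | 76% | 83% |

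By normal approximation, 80% power with 34 treated needs 29 historical patients.

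**5. Prospective XDR count.** The stated 38 is 880×4.3% = 37.8, which applies the South African rate to all three countries. By country it is 440×4.3% + 220×0.6% + 220×0.7% = 18.9+1.3+1.5 = 21.8, about 22. After 15% loss, 18 to 19 are evaluable.

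**6. What the prospective patients can support alone.**

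- Estimate: 29 of 34 (85%) has a Wilson 95% interval of 70% to 94%.
- Exact one-sample test against 53%, two-sided 5%, true rate 85%: 34 evaluable (reject at 25 or more) 98% power; 19 evaluable (15 or more) 86%; 18 evaluable (15 or more) 72%.

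**The case against.** The strongest reply is that the 40 is correct as a count of prospective enrolments. It reproduces exactly as a per-group size, the surrounding sentences count only prospective patients, and section 9.1 also gives only prospective numbers for the primary endpoints. On that reading, total means all sites together. This stands in part: the number itself is not a miscalculation, and the 52% from splitting it in two describes a design the text need not mean. But a per-group size is sufficient only with a partner group of similar size, and none is sized.

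A second reply is that the sentence names no comparator, and that section 9.2 speaks only of calculating proportions by resistance type, which is not a powered test. That is fair. The historical comparator is inferred from the endpoint that section 9.1 says it is powering. Even so, the one alternative, a fixed 53%, does not lead to 40 either, although 40 would be more than enough for it.

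A reader might go further and infer that the historical cohort certainly cannot supply the comparison, with only 4 to 22 patients available. The documents do not support that. The 40 are BPaL recipients, including pre-XDR and treatment-intolerant MDR patients. A like-for-like historical group would include them too, and the protocol gives no rate for them. The upper figure of 22 also needs a cohort 3 as large as cohort 1.

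Reading Table 1 as 220 at each of 13 sites would give about 35 XDR patients (440×4.3% + 1,320×0.6% + 1,100×0.7%) and remove the shortfall. That would take 1,100 records from five Ethiopian sites, against 658 RR/MDR cases reported nationally for 2019 in section 2.2, so it is hard to sustain. Nor can it be said that the 53% describes XDR: no case definition is given.

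**Conclusion.** The point holds as a fault in a secondary subgroup statement. Forty is a per-group size, a two-group comparison needs about 76 to 80, and the historical side is unsized. Restricted to XDR, the stated n=220 yields about 3 to 9 historical patients, depending on the assumed country split. With 4 to 9 of them and 34 evaluable treated, power is 28% to 48% by Fisher's exact test or 38% to 54% by normal approximation. Even about 22 historical XDR patients leave it below 80% by either method. For the wider BPaL-eligible group, adequacy cannot be judged from the protocol. The expected 38 prospective XDR cases should be about 22, so reaching 40 relies more on non-XDR patients than the text suggests.

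These results assume alpha of 5% and the quoted XDR rates. Those rates come from 2018 and 2019 reports, whereas section 3 adopts the 2021 definitions. Neither primary endpoint nor the primary sample size is affected.

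**What to change.** Rewrite the XDR and BPaL sentences of section 9.1:

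- Describe 40 as prospective BPaL participants (34 evaluable), not as the size of a two-group comparison.
- Report the BPaL success proportion as an estimate with a 95% confidence interval (about 70% to 94% if 85% is observed). Alternatively, specify a one-sample test against a pre-stated 53%, with its source, case definition, alpha and power. The reference must apply to the same case mix as the participants tested: power is about 98% with 34 evaluable, but about 72% to 86% if only the 18 to 19 evaluable XDR cases qualify.
- Label any comparison with historical patients of the same resistance type as descriptive.
- Replace the expected 38 XDR cases with about 22, computed by country.

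The cost is a few sentences and a more modest claim. No extra patients are needed.
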